7. INVESTIGATOR REQUIREMENTS

7.1 RETENTION OF RECORDS

FDA regulations (21 CFR §312.62[c]) and the ICH Guideline for GCP (see Section 4.9 of the guideline) require that records and documents pertaining to the conduct of clinical trials and the distribution of investigational drug, patient records, consent forms, laboratory test results, and medication inventory records, must be retained for 2 years after the last marketing application approval in an ICH region or after at least 2 years have elapsed since formal discontinuation of clinical development of the investigational product. All state and local laws for retention of records also apply.

For studies conducted outside the U.S. under a U.S. IND, the Principal Investigator must comply with the record retention requirements set forth in the FDA IND regulations and the relevant national and local health authorities, whichever is longer.

7.2 STUDY MEDICAL MONITORING REQUIREMENTS

This clinical research study will be monitored both internally by the PI and externally by the Icahn School of Medicine IRB. In terms of internal review, the PI will continuously monitor and tabulate AEs. Appropriate reporting to the Icahn School of Medicine IRB will be made. The PI of this study will also continuously monitor the conduct, data, and safety of this study to ensure that:

- Stopping rules for toxicity and/or response are met,
- Risk/benefit ratio is not altered to the detriment of the patients,
- Appropriate internal monitoring of AEs and outcomes is done,
- Over-accrual does not occur,
- Under-accrual is addressed with appropriate amendments or actions, and
- Data are being appropriately collected in a reasonably timely manner.

Routine monitoring will be carried out via a periodic team conference among investigators during which toxicity data, including all SAEs, will be reviewed and other issues relevant to the study such as interim assessment of accrual, outcome, and compliance with study guidelines, will be discussed. Monitoring will be carried out on an ongoing basis. The severity, relatedness, and whether or not the event is expected will be reviewed.

7.3 STUDY MEDICATION ACCOUNTABILITY

The Sponsor Investigator of the study will ensure maintenance of complete and accurate records of the receipt, dispensation, and disposal or return of all study drug in accordance with 21 Code of Federal Regulations (CFR), Part 312.57 and 312.62 and Genentech requirements.

All unused remaining product at the end of the study should be disposed of at the study site according to institutional standard operating procedure. If there is no SOP at the site for drug destruction, return study drug with the Inventory of Returned Clinical Material form as directed by Genentech.

7.4 DATA COLLECTION

The study coordinator and investigators are responsible for ensuring that the eligibility checklist is completed in a legible and timely manner for every patient enrolled in the study, and that data are recorded on the appropriate forms and in a timely manner. Any errors on source data should be lined through, but not obliterated, with the correction inserted, initialed, and dated by the study coordinator or PI. All source documents will be available for inspection by the FDA and the Icahn School of Medicine IRB.

7.5 DATA MONITORING

The entire study will be conducted using an electronic data acquisition method where all clinical data on enrolled subjects will be data entered (single-keyed) by the site personnel into a web-based data management system, REDCap. In order to provide user-friendly and easy-to-navigate interfaces, the REDCap data capture screens are designed based upon individual CRFs. Prior to study start, the system is validated to ensure the data entry screens mirror the CRFs and that the pre-programmed data rules appropriately detect incorrect data. The data will be managed after data entry via data queries from the study monitor. Monitoring will be conducted in real time, allowing for early identification of adverse events and protocol Tenecteplase-Icahn School of Medicine at Mount Sinai Protocol ML42492

deviations. This user-friendly web-based database system, developed and validated by the study team, will be used for subject data entry, data validation, project progress monitoring, subject tracking, coordination of safety review, randomization, user customizable report generation and secure data transfer.

8. ETHICAL CONSIDERATIONS

8.1 COMPLIANCE WITH LAWS AND REGULATIONS

Patients who comply with the requirements of the protocol, are tolerating study treatment, and may be receiving benefit will be offered dosing beyond Cycle 1 at the investigator's discretion after a careful assessment and thorough discussion of the potential risks and benefits of continued treatment with the patient. Such patients may have the option to receive MPDL3280A treatment as long as they continue to experience clinical benefit in the opinion of the investigator until the earlier of unacceptable toxicity, symptomatic deterioration attributed to disease progression, or any of the other reasons for treatment discontinuation listed in [Section 4.6](#).

8.2 INFORMED CONSENT

The informed consent document must be signed by the patient or the patient's legally authorized representative before his or her participation in the study. The case history for each patient shall document that informed consent was obtained prior to participation in the study. A copy of the informed consent document must be provided to the patient or the patient's legally authorized representative. If applicable, it will be provided in a certified translation of the local language.

Signed consent forms must remain in each patient's study file and must be available for verification by study monitors at any time.

8.3 INSTITUTIONAL REVIEW BOARD OR ETHICS COMMITTEE

This protocol, the informed consent document, and relevant supporting information must be submitted to the IRB for review and must be approved before the study is initiated. The study will be conducted in accordance with FDA, applicable national and local health authorities, and IRB requirements.

The Principal Investigator is responsible for keeping the IRB apprised of the progress of the study and of any changes made to the protocol as deemed appropriate, but in any case, the IRB must be updated at least once a year. The Principal Investigator must also keep the IRB informed of any significant AEs.

Investigators are required to promptly notify their respective IRB of all adverse drug reactions that are both serious and unexpected. This generally refers to SAEs that are not already identified in the Investigator's Brochure and that are considered possibly or probably related to the tenecteplase or study drug by the investigator. Some IRBs may have other specific AE requirements to which investigators are expected to adhere. Investigators must immediately forward to their IRB any written safety report or update provided by Genentech (e.g., IND safety report, Investigator's Brochure, safety amendments and updates, etc.).

Tenecteplase–Icahn School of Medicine at Mount Sinai
Protocol ML42492

40

8.4 CONFIDENTIALITY

Patient medical information obtained by this study is confidential and may be disclosed to third parties only as permitted by the ICF (or separate authorization to use and disclose personal health information) signed by the patient or unless permitted or required by law.

Medical information may be given to a patient's personal physician or other appropriate medical personnel responsible for the patient's welfare for treatment purposes.

Data generated by this study must be available for inspection upon request by representatives of the FDA and other regulatory agencies, national and local health authorities, Genentech representatives and collaborators, and the IRB/Ethics Committee (EC) for each study site, if appropriate.


Tenecteplase-Icahn School of Medicine at Mount Sinai
Protocol ML42492

45

Appendix 1

Study Flowchart

	Screening	Enrollment/Randomization ^a		Follow Up Period (Day 4 to 27 post randomization)	End of Study (Day 28 OR Discharge)
		Pre-Randomization (must be collected within 2 h of study drug administration)	Post Randomization q6 hr. to 72 hr.		
Informed Consent	x				
Demographics	x				
Medical History	x				
Inclusion/Exclusion Criteria	x	x			
Weight for Dosing	x				
Vital Signs ^b	x	x	x	x	x
PCR COVID Test	x				
Lab Testing ^c	x	x	x ^d	SOC	SOC
Arterial Blood Gas ^e	x	x	x [*]	SOC	
Respiratory Status/Ventilator Settings ^f	x	x	x	x ^{**}	x
Ordinal Scale	x	x	x	x	x
Neurological Exam ^g	x	x	x	x	x
Vasopressor Dosing	x	x	x	x	
TNK-tPA Dosing			x		
Heparin Dosing ^h	x***	x***	x	x	
Imaging ⁱ	SOC		SOC	SOC	SOC
Pregnancy Test ^j	x				
Adverse Events/ SAE Review ^k	x	x	x	x	x
Concomitant Medications	x	x	x	x	x

Tenecteplase–Icahn School of Medicine at Mount Sinai
Protocol ML42492

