2.2 PRIMARY EFFICACY OUTCOME

The primary efficacy outcome will be the proportion of patients alive and free of respiratory failure (defined as not requiring non-rebreather, high-flow nasal cannula, non-invasive positive pressure ventilation, or mechanical ventilation) at 28 days.

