4.5.6 End of Study (Day 28)

The following assessments will be collected at the final End of Study timepoint if the patient is still admitted:

- Neurological Exam

- Vitals

- Laboratory Samples (Standard of care)

Tenecteplase–Icahn School of Medicine at Mount Sinai
Protocol ML42492

20

Thromboelastograms (when available according to standard practice)

- Respiratory Status / Ventilator Settings
- Imaging (Standard of Care)
- Concomitant medication review (excluding “prn” or “as needed” medications)

The ordinal scale assessment will be completed at day 28 regardless of whether the patient is admitted or discharged.

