5.3.1 Adverse Event Reporting Period

The study period during which all AEs and SAEs must be reported begins after informed consent is obtained and initiation of any study procedures and ends 28 days following the last administration of study treatment or study discontinuation/termination, whichever is earlier. After this period, investigators should only report SAEs that are attributed to prior study treatment.

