6.2 PRIMARY EFFICACY VARIABLE

Data will be analyzed according to clinical status at day 28. Outcome will be the proportion of patients who are alive and free of respiratory failure (no use of HFNC, NIPPV, Intubation). All other patients, those on HFNC, NIPPV, or mechanical ventilation, or dead, will be assessed as

Tenecteplase-Icahn School of Medicine at Mount Sinai
Protocol ML42492

37

failures for the purposes of the primary analysis. In the case of missing data, a last carry forward methodology will be used.

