- j. A woman is considered to be of childbearing potential if she is postmenarcheal, has not reached a postmenopausal state (\geq 12 continuous months of amenorrhea with no identified cause other than menopause), and has not undergone surgical sterilization (removal of ovaries and/or uterus). Urine/serum pregnancy test: all women of childbearing potential will have a pregnancy test at screening. If a urine pregnancy test is positive, it must be confirmed by a serum pregnancy test.
- k. All AEs that occur after signing the ICF and up to the EOS visit must be recorded. AESI's for this study protocol include: bleeding, hypersensitivity, thromboembolism, cholesterol embolization and arrhythmias. post-permanent SD discontinuation.
 - * To be performed q12h.
 - ** To be performed daily until a 2 point improvement in the ordinal scale assessment OR until 27 days OR until death OR discharge.
 - *** For patients already on heparin.

Tenecteplase—Icahn School of Medicine at Mount Sinai
Protocol ML42492

47

Effective Date: 6/15/2021

End Date: 12/7/2021

Appendix 2

Safety Reporting Fax Cover Sheet

A Member of the Roche Group

SAFETY REPORTING FAX COVER SHEET

GENENTECH SUPPORTED RESEARCH

AE / SAE [contact]

Genentech Study Number	
Principal Investigator	
Site Name	
Reporter name	
Reporter Telephone #	
Reporter Fax #	

Initial Report Date	[DD] / [MON] / [YY]
Follow-up Report Date	[DD] / [MON] / [YY]

Patient Initials (Enter a dash if patient has no middle name)	[] - [] - []
--	-----------------

SAE or Safety Reporting questions, contact Genentech Drug Safety: [contact]

PLEASE PLACE MEDWATCH REPORT or SAFETY REPORT BEHIND THIS COVER SHEET

Appendix 3

FDA MedWatch 3500 Form

This form is included in the study start-up zip file to be sent to sites via email.

Tenetecplase-Icahn School of Medicine at Mount Sinai
Protocol **ML42492**

49

Effective Date: 6/15/2021

End Date: 12/7/2021

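### The Appendix 1 flowchart lets the study and AE recording end at discharge, contradicting Sections 4.5.6 and 5.3.1, so sites that follow it could lack Day-28 outcomes for discharged patients

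*Combined protocol and SAP*

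**What the plan says.** Section 2.2 makes the primary efficacy outcome "the proportion of patients alive and free of respiratory failure" at 28 days, and Section 6.2 states "Data will be analyzed according to clinical status at day 28". Section 2.3 lists 28-day mortality separately from 14-day in-hospital mortality, so the former is not confined to inpatients. Section 6.3 counts intracranial and major bleeding up to Day 28.

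On follow-up, the documents give two schedules. The Appendix 1 flowchart closes with a column headed "End of Study (Day 28 OR Discharge". Its footnote k says "All AEs that occur after signing the ICF and up to the EOS visit must be recorded". Section 4.5.6 sets the end-of-study visit at Day 28 and says "The ordinal scale assessment will be completed at day 28 regardless of whether the patient is admitted or discharged". The rest of that visit, including respiratory status and ventilator settings, is conditional: "The following assessments will be collected at the final End of Study timepoint if the patient is still admitted". Section 5.3.1 has an adverse event period that "ends 28 days following the last administration of study treatment or study discontinuation/termination, whichever is earlier".

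For gaps in the primary outcome, Section 6.2 says "In the case of missing data, a last carry forward methodology will be used".

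**The concern.** Section 4.5 points sites to Appendix 1 as the schedule of activities, so its column heading is likely to drive what is done at the bedside. Under that heading, a patient who goes home on Day 10 has the final visit on Day 10, and no later column exists. The primary outcome, 28-day mortality and the Section 6.3 safety variable all need to know what happened between then and Day 28.

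If nobody asks, Section 6.2 fills the gap with the last recorded status. For a discharged patient that is usually alive and off support. A death at home or a readmission on respiratory support would then be counted as a success, and a late bleed would not be counted. Status that was never recorded may not be recoverable at analysis.

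**Working it through.** **The two schedules side by side**

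| Item | Appendix 1 | Body of the protocol |
|---|---|---|
| Final visit | Day 28 or discharge | Day 28 (4.5.6) |
| Ordinal scale after discharge | none after the final visit | required at Day 28 (4.5.6) |
| Respiratory status and settings | daily item stops at discharge, or sooner after a 2-point improvement; then at the final visit | at Day 28 only if still admitted (4.5.6) |
| Adverse events | to the final visit (footnote k) | 28 days after dosing, or discontinuation/termination if earlier (5.3.1) |

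A site cannot follow both columns for a patient discharged before Day 28. Two cases follow.

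1. *The site follows the flowchart.* There is no Day-28 status, so the 6.2 rule applies and discharge status becomes the outcome.
2. *The site follows 4.5.6.* A Day-28 ordinal score exists and nothing is carried forward. The score settles the primary outcome if its levels separate NRB, HFNC, NIPPV and ventilation from no such support. The levels are not in the supplied text. If the Day-28 contact is missed, the patient falls back into case 1.

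**The plan's own figure.** Section 6.1 states about 70% power for 50% against 15% (40 against 20 patients, Fisher's exact test, two-sided 0.05). Exact enumeration gives 74.5% with the usual two-sided p-value and 71.4% with a doubled one-sided p-value. This point neither disputes that figure nor depends on it.

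**Size in case 1.** The documents give no discharge or relapse rates, so both are assumed: 30–50% of patients discharged before Day 28, and 3–10% of those dead or back on support by Day 28. The formula is patients × share discharged × share failing later.

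- Low: 60 × 0.30 × 0.03 = 0.54
- High: 60 × 0.50 × 0.10 = 3.0

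One patient is 1/20 = 5 percentage points in a 20-patient arm and 1/40 = 2.5 points in the combined arm, against a design difference of 35 points.

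**A second illustration.** Take the design rates as true and let r be the assumed share of apparent successes at discharge who are failures by Day 28, equal in both groups. The observed rate is the true rate / (1 − r). The number misscored is 20 × (observed − 0.15) + 40 × (observed − 0.50), using each group's own observed rate.

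| r | Control | Combined | Difference | Misscored of 60 |
|---|---|---|---|---|
| 0 | 15.0% | 50.0% | 35.0 points | 0 |
| 5% | 15.8% | 52.6% | 36.8 | 1.2 |
| 10% | 16.7% | 55.6% | 38.9 | 2.6 |
| 20% | 18.75% | 62.5% | 43.75 | 5.75 |

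This treats every success as scored at discharge, so it is an upper illustration. If the true rates were equal and r were equal, the observed difference would stay at zero.

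**The case against.** The strongest reply is that the body of the protocol already plans a Day-28 status for everyone. Section 4.5.6 is explicit, the ordinal scale is described in 4.5.2 as the measure of current status, and carry-forward applies only when data are missing. This stands. A reader might infer that the plan scores discharged patients on discharge status by design. It does not. That happens only if a site works from the flowchart alone or the Day-28 contact fails.

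A reader might also infer that respiratory support is never collected at Day 28 after discharge. The documents do not establish this. The item restricted to inpatients consists largely of bedside settings (rates, pressures, FiO2, flow), which cannot apply to someone at home without support, and the ordinal scale may capture support.

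Deaths have other routes. Section 5.1.1 halts enrollment for any death in the 28-day follow-up, and Section 5.4.3.2 requires all deaths in the reporting period to be reported. These are duties to act on a known death. The flowchart gives no contact through which a death at home would become known, and the public-records provision in 4.6.1 covers withdrawn patients only. So they reduce the risk without closing it.

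On safety, Section 2.3 sets a 72-hour window for the primary safety outcome, so loss of late bleeds matters only under Section 6.3. That also stands, and the two windows need separate reconciliation.

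Finally, the trial is stated not to be powered for significance, and few controls are exposed: 0.15 × 20 = 3 expected successes. This limits the size but does not remove the contradiction.

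**Conclusion.** The contradiction is real and should be corrected. Appendix 1 and its footnote k cannot be reconciled with Sections 4.5.6 and 5.3.1 for a patient discharged before Day 28. A site following the flowchart would leave Section 6.2 to supply the primary outcome from discharge status.

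The size cannot be determined from the documents. Under the assumed rates it is about 0.5 to 3 of 60 patients, and only if every site followed the flowchart throughout. If the control rate held in all arms, only 0.15 × 60 = 9 patients would be Day-28 successes, so early discharges, and with them the number at risk, would probably be below that range.

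The usual direction is towards success, but it is not strictly one-way: a patient sent home on support who later recovers would be wrongly scored a failure. A reader might infer a bias in favour of tenecteplase. That would need earlier discharge or a higher true success rate on tenecteplase, and the documents supply no data on either.

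**What to change.** 1. Retitle the last column of Appendix 1 *End of Study, Day 28, all patients*.
2. Align footnote k with Section 5.3.1 so that adverse event recording does not end at discharge.
3. At the Day-28 contact that 4.5.6 already requires, record for discharged patients: vital status with date of death; current respiratory support (NRB, HFNC, NIPPV, ventilation or none); readmission; and bleeding or other adverse events since discharge. Bedside ventilator settings can stay limited to inpatients.
4. State in 6.2 that discharge status is not carried forward as the Day-28 outcome. Report the number with unknown Day-28 status by arm, with a best-case/worst-case sensitivity analysis.

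The cost is a few wording changes and a few more questions at an existing contact. Sample size, significance level and treatment are unchanged. Some discharged patients may be unreachable and would remain unknown, which the sensitivity analysis would show openly.

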Appendix 1: Study Flowchart

- a. Randomization will be done using an escalating-dose randomized design. It will be block randomization of 10:5 (treatment:control) performed twice per dose of TNK-tPA. If no safety triggers occur after 20 patients enrolled at the low dose, then the high dose enrollment will be undertaken with block randomization of 10:5.
- b. Vital signs include respiratory rate, pulse rate, systolic and diastolic blood pressure and temperature. Vitals are to be measured within 60 minutes prior to each tenecteplase infusion and, if clinically indicated, during or after the infusion.
- c. Labs to be collected include: CBC: Platelet, WBC, Hb, Hct; BMP: Na, K, Cl, HCO3, BUN, Cr; Glucose (finger stick or lab); LFT: ALT, AST, Bili, Alk Phos, LDH, Total Protein, Albumin, D-dimer, fibrinogen, CRP, ferritin, troponin-I; Coagulation: INR, aPTT, Anti-Xa, PT (only if the patient is taking an anticoagulant); Thromboelastograms
- d. Only coagulation labs need to be checked every 6 hours post randomization which includes: INR, aPTT, PT (only if the patient is taking an anticoagulant)
- e. Arterial blood gases to be collected include: Arterial Blood Gas: pH, pCO2, pO2, SaO2, Lactate
- f. Ventilator/Respirator Setting settings to be collected include: RR, TV, PEEP, Plateau Pressure; NIPPV settings (if appropriate): RR, IPAP, EPAP, FiO2; HFNC settings (if appropriate): FiO2, flow
- g. Neurological exams are to be performed every time room access is breached.
- h. For patients already on therapeutic heparin, continue heparin infusion. For patients not already on heparin or other anticoagulant, begin heparin with tenecteplase infusion starting with bolus dose of 60 Units/kg IV once, followed by 12 Units/kg/hr. For patients who were receiving enoxaparin at time of inclusion, tenecteplase infusion can be given immediately. Delay heparin to 12 hours after the most recent enoxaparin dose, beginning at an infusion rate of 18 Units/kg/hr. Do not administer a bolus dose of heparin and check PTT every 6 hours; adjust heparin to achieve target PTT of 70-90 seconds.
- i. All image collection should follow institution specific standard of care guidelines.
- j. A woman is considered to be of childbearing potential if she is postmenarcheal, has not reached a postmenopausal state (\geq 12 continuous months of amenorrhea with no identified cause other than menopause), and has not undergone surgical sterilization (removal of ovaries and/or uterus). Urine/serum pregnancy test: all women of childbearing potential will have a pregnancy test at screening. If a urine pregnancy test is positive, it must be confirmed by a serum pregnancy test.
- k. All AEs that occur after signing the ICF and up to the EOS visit must be recorded. AESI's for this study protocol include: bleeding, hypersensitivity, thromboembolism, cholesterol embolization and arrhythmias. post-permanent SD discontinuation.
 - * To be performed q12h.
 - ** To be performed daily until a 2 point improvement in the ordinal scale assessment OR until 27 days OR until death OR discharge.
 - *** For patients already on heparin.

Tenecteplase—Icahn School of Medicine at Mount Sinai
Protocol ML42492

47

Effective Date: 6/15/2021

End Date: 12/7/2021

Appendix 2

Safety Reporting Fax Cover Sheet

A Member of the Roche Group

SAFETY REPORTING FAX COVER SHEET

GENENTECH SUPPORTED RESEARCH

AE / SAE [contact]

Genentech Study Number	
Principal Investigator	
Site Name	
Reporter name	
Reporter Telephone #	
Reporter Fax #	

Initial Report Date	[DD] / [MON] / [YY]
Follow-up Report Date	[DD] / [MON] / [YY]

Patient Initials (Enter a dash if patient has no middle name)	[] - [] - []
--	-----------------

SAE or Safety Reporting questions, contact Genentech Drug Safety: [contact]

PLEASE PLACE MEDWATCH REPORT or SAFETY REPORT BEHIND THIS COVER SHEET

Appendix 3

FDA MedWatch 3500 Form

This form is included in the study start-up zip file to be sent to sites via email.

Tenetecplase-Icahn School of Medicine at Mount Sinai
Protocol **ML42492**

49

Effective Date: 6/15/2021

End Date: 12/7/2021

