3.3.1 Rationale for Tenecteplase Dose and Schedule

Tenecteplase is a triple combination mutant of alteplase, with a longer half-life, improved specificity for fibrin, and higher resistance to degradation by plasminogen-activator inhibitor.²² One practical clinical advantage over other thrombolytic drugs is the ability to bolus a single dose of tenecteplase, compared to longer infusions required for efficacy (i.e. alteplase). Tenecteplase was first studied in acute myocardial infarction (AMI) in the 1990s. In the TIMI 10A trial, tenecteplase was found to be effective for coronary reperfusion in patients with AMI and had a safety profile comparable to wild-type tPA.²³ The follow up TIMI 10B trial randomized 886 patients with early (≤ 12 hr) AMI to either bolus tenecteplase or bolus + infusion of tPA, plus coronary angiography and postprocedural heparin infusion.²⁴ The study authors found that overall rates of TIMI grade 3 reperfusion were similar between the two groups, but this finding was found in patients who received higher doses of tenecteplase (50 mg versus 30 mg), albeit with higher risk of symptomatic bleeding and intracranial hemorrhage. The risks of hemorrhage were reduced in both groups by lowering heparin infusion rates. A further safety assessment of tenecteplase, relative to alteplase, was published in 1999 through the ASSENT-1 trial, in which a total of 325 patients were given a single bolus of tenecteplase in escalating doses (30, 40, or 50 mg).²⁵ Overall rates of intracranial hemorrhage were low (0.77% overall), did not depend on dose, and were comparable to historical data on tPA. Overall, the authors recommend a weight-based dosing strategy for patients with AMI.

Based on these positive safety trials, subsequent trials were published directly comparing tenecteplase and alteplase. ASSENT-2 was a double-blind, controlled trial randomizing 16,949 patients to either weight based tenecteplase bolus (0.5 mg/kg) or infusion with tPA, plus aspirin and heparin infusion.²⁶ The primary outcome of all-cause mortality at 30 days was similar for the two groups (6.18% and 6.15% for tenecteplase and tPA, respectively). Rates of intracranial hemorrhage were also similar between the two groups, although the risk of other hemorrhage was higher for tPA.

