Tenecteplase has also been assessed for use in treating pulmonary embolism (PE). In general, thrombolysis for PE has been shown to have minimal evidence for clinical benefit compared with heparin, except in those with the highest risks of recurrence or death.³² In clinical trials, thrombolysis with alteplase has been associated with improvements in hemodynamic parameters (including pulmonary resistance and cardiac index) but have indeterminate effects on overall clinical outcomes given a paucity of data.³³ In one randomized, placebo-controlled trial of tenecteplase (at a dose of 0.5 mg/kg) plus heparin versus heparin alone, intermediate-risk patients with PE treated with TNK had lower risk of hemodynamic decompensation or death.³⁴ Symptomatic intracranial hemorrhage was more frequent in the TNK group, though occurred predominantly in patients older than 75 years old. Patients with submassive PE have also been found to have increased odds of good outcome after treatment with tenecteplase, compared with placebo, according to a randomized trial published in 2014.³⁵

Based on this evidence, dosing guidelines for this trial will be as follows:

Patients will be monitored in the ICU immediately post-treatment and until 24 hours have passed and they are considered stable to downgrade to lower level of care.

- A. For patients already on therapeutic heparin, continue heparin infusion
- B. For patients not already on heparin or other anticoagulant, begin heparin with tenecteplase infusion starting with bolus dose of 60 Units/kg IV once (maximum dose of 5000 Units), followed by 12 Units/kg/hr (patients will only receive one dose of tenecteplase in total)
- C. For patients who were receiving enoxaparin at time of inclusion, tenecteplase infusion can be given immediately. Delay heparin to 12 hours after the most recent enoxaparin dose, beginning at an infusion rate of 12 Units/kg/hr. Do not administer a bolus dose of heparin.

-Check PTT every 6 hours; adjust heparin to achieve target PTT between 2 and 2.5 times ULN

Tenecteplase–Icahn School of Medicine at Mount Sinai
Protocol ML42492

12

Patients will continue with the unfractionated heparin infusion for 24 hours from the beginning of the study. After 24 hours, they may be transitioned to low molecular weight heparin according to institutional standard of care.

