4.3 STUDY TREATMENT

The investigational medicinal product (IMP) for this study is tenecteplase. This will be given to patients in combination with heparin, as outlined in section 3.3.1.

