4.3.2 Study Treatment Dosage, Administration, and Compliance

The treatment regimens are summarized in Section 3.3.1.

Any overdose or incorrect administration of tenecteplase or placebo should be noted in the patient's medical records and reported according to Section 5.5 (Special Situations Reports). Adverse events associated with an overdose or incorrect administration of any of the study treatments should be recorded in the patient's medical records.

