4.5 STUDY ASSESSMENTS AND PROCEDURES

The schedule of activities to be performed during the study is provided in Appendix 1. All activities must be performed and documented for each patient. Patients will be closely monitored for safety and tolerability throughout the study. Patients should be assessed for toxicity prior to each dose; dosing will occur only if the clinical assessment and local laboratory test values are acceptable.

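### Patients on enoxaparin at inclusion start heparin at 12 Units/kg/hr under Section 3.3.1 but at 18 Units/kg/hr under Appendix 1 footnote h, and nothing says which governs

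*Combined protocol and SAP*

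**What the plan says.** Section 3.3.1 sets heparin dosing by anticoagulant status at entry. For patients on enoxaparin, item C reads "Delay heparin to 12 hours after the most recent enoxaparin dose, beginning at an infusion rate of 12 Units/kg/hr", with no bolus.

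In Appendix 1 the Heparin Dosing row carries footnote h, which for the same patients reads "Delay heparin to 12 hours after the most recent enoxaparin dose, beginning at an infusion rate of 18 Units/kg/hr", again with no bolus. Both are current text; neither comes from an amendment history.

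The cross-references point both ways:

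- Section 4.3, on the study drug: "This will be given to patients in combination with heparin, as outlined in section 3.3.1".
- Section 4.3.2: "The treatment regimens are summarized in Section 3.3.1". Section 4.3.2.1 also refers to 3.3.1 for dosing.
- Section 4.5: "The schedule of activities to be performed during the study is provided in Appendix 1". It adds that every activity is to be carried out and documented for each patient.

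Section 4.5.4 spells out heparin dosing only for patients not previously on heparin, so it does not settle the enoxaparin rate.

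Two smaller differences sit in the same text. For patients on no anticoagulant, Section 3.3.1 gives a "bolus dose of 60 Units/kg IV once (maximum dose of 5000 Units), followed by 12 Units/kg/hr"; Section 4.5.4 and footnote h repeat the bolus without the cap. The PTT target is 2 to 2.5 times ULN in Section 3.3.1 but 70 to 90 seconds in Section 4.5.4 and footnote h.

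**The concern.** Footnote h is a complete dosing instruction on the page that bedside staff are most likely to use. Section 3.3.1 is titled as a rationale. Someone working from the flowchart has no prompt to look there and find a different rate.

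The patients concerned have recent enoxaparin on board and, with 2:1 randomization, have probably just received a thrombolytic. Sections 4.4.1 and 5.1.3.3 warn that anticoagulants around tenecteplase may raise bleeding risk. Section 3.3.1, describing an earlier myocardial infarction trial, reports "The risks of hemorrhage were reduced in both groups by lowering heparin infusion rates". The first hours of infusion fall inside the 72-hour window for intracranial or major bleeding, which is the primary safety outcome in Section 2.3. The safety trigger in Section 4.2 is a difference of more than two patients between arms, so single bleeding events carry weight.

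**Working it through.** **Side by side**

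| Patients at entry | Section 3.3.1 | Section 4.5.4 | Appendix 1 footnote h |
|---|---|---|---|
| On therapeutic heparin | continue infusion | no separate rate | continue infusion |
| On no anticoagulant | 60 Units/kg bolus (cap 5000), then 12/kg/hr | 60 Units/kg bolus (no cap), then 12/kg/hr | 60 Units/kg bolus (no cap), then 12/kg/hr |
| On enoxaparin | no bolus, **12**/kg/hr | no enoxaparin rate | no bolus, **18**/kg/hr |

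The rate conflict is confined to the enoxaparin row.

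**Size of the rate difference.** The documents give no body weights, so these are assumed.

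- Ratio: 18/12 = 1.5.
- 60 kg: 1080 v 720 Units/hr. 80 kg: 1440 v 960. 100 kg: 1800 v 1200.

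**Excess before correction.** Both texts check PTT every 6 hours. If the first adjustment comes *t* hours after heparin starts, the excess is (18 − 12) × *t* Units/kg.

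- *t* = 6 h: 36 Units/kg, or 2880 Units at 80 kg and 3600 at 100 kg.
- *t* = 3 h: 18 Units/kg, or 1440 Units at 80 kg.
- As a yardstick, 36/60 = 60% of the bolus these patients are told not to receive.

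**Share of the mandated infusion.** Section 3.3.1 says "Patients will continue with the unfractionated heparin infusion for 24 hours from the beginning of the study". If the last enoxaparin dose was 0 to 12 hours before study start, heparin begins 12 to 0 hours after it and so runs for 12 to 24 of those 24 hours. Six hours is then 6/24 = 25% to 6/12 = 50% of the required infusion.

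**Bolus cap.** 5000/60 = 83.3 kg, so the missing cap matters only above that weight: 60 × 90 = 5400 Units (+8%); 60 × 100 = 6000 (+20%).

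**PTT target.** The documents give no ULN, so a range is assumed. The two windows overlap when 2 × ULN ≤ 90 and 2.5 × ULN ≥ 70, that is, for ULN from 28 to 45 s.

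| Assumed ULN (s) | 2 to 2.5 × ULN (s) | Overlap with 70–90 s |
|---|---|---|
| 30 | 60–75 | 70–75 |
| 35 | 70–87.5 | 70–87.5 |
| 40 | 80–100 | 80–90 |
| 45 | 90–112.5 | 90 only |

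They nearly coincide only at about 35 to 36 s (2 × 35 = 70; 2.5 × 36 = 90). Neither target is lower at every ULN.

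**The case against.** The best counter-argument is that the intended rate is easy to infer. Section 4.3 names Section 3.3.1 specifically for heparin, Section 4.5 names Appendix 1 only for the schedule, and 18 appears once while every other stated rate is 12. That supports 12 as the correction. It does not make footnote h safe to follow as printed.

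Second, the bolus comparison shows one side. Over 6 hours footnote h delivers 18 × 6 = 108 Units/kg. The undisputed regimen for patients on no anticoagulant delivers 60 + 12 × 6 = 132, so footnote h is 24/132 = 18% lower and does not catch up until 60/6 = 10 hours. At 100 kg with the cap it is 10,800 against 12,200 Units, with crossover at 5000/600 = 8.3 hours. This stands, and it argues against calling the higher rate extreme. However, those patients have no recent enoxaparin, and the plan deliberately gives the enoxaparin group no bolus.

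Third, 6 hours is close to an upper bound. Section 4.5.4 times coagulation tests from study drug administration, so the first PTT after a delayed heparin start may come anywhere from 0 to 6 hours in. This also stands, and the excess before correction is therefore better read as up to 36 Units/kg. Titration is still an imperfect safeguard: a sample drawn soon after the start says little about the rate, and Section 5.1.3.4 warns that coagulation results may be unreliable during tenecteplase therapy.

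Finally, the sentence on lower heparin rates comes from a different disease and gives no rates, so it supports the direction of risk only. The bolus cap and PTT target are separate, lesser points; Section 4.5.4 refers back to the protocol for starting the infusion, which arguably recovers the cap.

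**Conclusion.** The concern holds. Two current instructions give the same patients starting heparin rates that differ by 50%, and no clause ranks them. The ratio needs no assumption. The excess of up to 36 Units/kg assumes a first adjustment no later than 6 hours after heparin starts, and the absolute doses assume body weight.

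The consequence is a patient-safety risk and possibly some noise in a small bleeding count. No bias between arms is expected, because treatment is blinded and randomization is stratified by site. No sample size, power or efficacy figure changes. The documents do not give the share of patients on enoxaparin, so the number affected and any excess of bleeding cannot be estimated. The existence of a dedicated dosing branch shows that such patients were expected. Given the drug combination and the low cost of correction, this should be put right before another such patient is treated.

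**What to change.** 1. State that Section 3.3.1 governs heparin dosing and that Appendix 1 only summarises it.
2. In footnote h, change 18 to 12 Units/kg/hr. If the clinical leads confirm that 18 was intended, correct Section 3.3.1 item C instead.
3. Add the 5000-Unit maximum to the bolus text in Section 4.5.4 and footnote h.
4. Use one PTT target in Section 3.3.1, Section 4.5.4 and footnote h. With Section 3.3.1 governing, the default is 2 to 2.5 times the local ULN; this is a clinical choice, and if 70 to 90 seconds was meant, Section 3.3.1 should change. Align the aPTT trigger in Section 4.5.5 with the choice; it is a recording rule, not a dosing rule.
5. For enoxaparin patients already treated, list the starting rate used. Appendix 1 already schedules heparin dosing data, so this should mainly need extraction.

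The cost is a wording amendment and a site memo.
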